5.1.2 Exclusion criteria

1. Subject previously underwent a fallopian tube sterilization procedure (other than Essure placement)
2. Subject is pregnant or desires to become pregnant in the future
3. Subject only has one Essure micro-insert placed
4. Subject's Essure Confirmation Test was performed less than three months (up to 1 week prior to 3 months is considered acceptable) from the date of Essure placement¹⁷
5. Subject is currently wearing an intrauterine device or intrauterine system and is unwilling to have it removed before the NovaSure EA procedure¹⁸
6. Subject has undergone any intrauterine procedure in between Essure placement procedure and NovaSure EA. Endometrial biopsy or sampling if required or indicated is permitted. Intrauterine device/intrauterine system (IUD/IUS) removal is permitted. Procedures which permit direct visualization of the inserts while assessing the

¹⁵ TVU confirmation testing criteria added per Amendment 6

¹⁶ Per Amendment 4

¹⁷ Per Amendment 5

¹⁸ Per Amendment 4

endometrium to ensure that menorrhagia is due to benign causes (e.g. saline infusion sonography or diagnostic hysteroscopy) are permitted [[6]]¹⁹

7. Subject is scheduled to undergo any other intrauterine procedures at the time of NovaSure EA (except endometrial biopsy or sampling, if required or indicated; IUD/IUS removal is permitted)²⁰
8. Subject presents with any other medical complaints, conditions or symptoms unrelated to the Essure System and/or subsequent NovaSure EA including, but not limited to:
 - Gynecological co-morbidities (e.g., pelvic infection, cervicitis, undiagnosed vaginal bleeding, endometrial cancer, pre-malignant conditions of the endometrium, myomas, and polyps)
 - Reproductive tract anatomical variants and/or pathology which could make the subject unsuitable for the Essure and/or NovaSure transcervical procedures (e.g. history of previous classical cesarean section, transmural myomectomy, pathological condition that could lead to weakening of the myometrium)
 - Active genital or urinary tract infection or pelvic inflammatory disease at time of procedure
 - Any other medical condition that precludes safe participation in the study, in the opinion of investigator
9. Subject who has participated in another clinical study in the 30 days prior to signing the informed consent for the PAS

5.2 Withdrawal of subjects from study²¹

5.2.1 Withdrawal²² - amended

Subjects *must* be withdrawn from the study for the following reasons:

- At their own request or at the request of their legally acceptable representative
- At any time during the study and without giving reasons, a subject may decline to participate further. The subject will not suffer any disadvantage as a result.
- If, in the investigator's opinion, continuation of the study would be harmful to the subject's well-being

Subjects may be terminated from the study by the Investigator. Reasons for termination of a subject from the study may include, but are not limited to, the following:

- Subject does not retain device (e.g. due to removal of device, expulsion, salpingectomy or other utero-tubal surgeries)

¹⁹ Per Amendment 4 and 5

²⁰ Per Amendment 4

²¹ New section from sponsor template per Amendment 4

²² Withdrawal criteria adapted to suit a device meant for permanent wearing per Amendment 6.

- Death
- An adverse event (AE) preventing study participation
- Lost to follow-up and inability to contact the subject. Note that if a subject who is lost to follow-up is re-contacted, the subject will not be considered to have withdrawn from the study.

A subject who discontinues study participation prematurely for any reason is defined as a “dropout” if the subject has already undergone the NovaSure procedure.

A subject who, for any reason (e.g. failure to satisfy the selection criteria), terminates the study before the time point used for the definition of “dropout” (see above) is regarded a “screening failure”.

Any subject removed from the trial will remain under medical supervision until discharge or transfer is medically acceptable.

In all cases, the reason for withdrawal must be recorded in the case report form (CRF) and in the subject's medical records.

Details for the premature termination of the study as a whole (or components thereof [e.g. centers, treatment arms, dose steps]) are provided in Section 10 (Premature termination of the study).

5.2.2 Replacement

Subjects will not be replaced if withdrawn or terminated from the study.

5.3 Subject identification²³

After subjects have signed the informed consent form (ICF), they will be identified by a unique 5-digit subject identification number. The subject identification number which will identify the subject throughout the study is constructed as follows:

- Digit 1-2: Study center number
- Digit 3-5: Subject number, unique within any study center. Sequential number reflecting the order in which the subjects signed the ICF at the center.

6. Treatment²⁴

6.1 Treatments to be administered

In this study, the NovaSure EA procedure following successful placement of a commercially available Essure device is the treatment being administered. The Essure device, with the exception of relatedness of AEs, and placement procedure are not being evaluated.

²³ New section from sponsor template per Amendment 4.

²⁴ New section from sponsor template (Section 6 populated with content from previous version of protocol) per Amendment 4.

6.2 Identity of study treatment

Not applicable.

6.3 Treatment assignment - *amended*

This is a non-randomized, continuous enrollment study in which all eligible subjects will be asked to enroll. To avoid selection bias, investigators will offer enrollment in the study to all eligible subjects consecutively (as they present themselves to the investigator).

A subject may not be enrolled in the study until she has a successful Essure confirmation test done that documents bilateral satisfactory device location and fallopian tube occlusion noted on HSG OR optimal or satisfactory micro-insert location noted on TVU. If subject has had Essure placement but she does not have an Essure Confirmation Test that documents bilateral satisfactory device location and fallopian tube occlusion on HSG OR optimal or satisfactory micro-insert location on TVU, she may repeat the Essure Confirmation Test.²⁵

6.4 Dosage and administration

Not applicable.

6.5 Blinding

Blinding will not occur in this study. Procedures for emergency unblinding are not required.

6.6 Device logistics and accountability

Not applicable.

6.7 Treatment compliance

The Essure device is intended for subjects who desire permanent contraception (female sterilization) and is not intended to be removed.

6.8 Post-study therapy

Not applicable.

6.9 Prior and concomitant therapy

Gynecological procedures and medications necessary for the subject's well-being will be allowed during the study. Any medical treatment administered for the treatment of AEs that occur during the study will be recorded in the CRF.

²⁵ TVU confirmation testing criteria added per Amendment 6

7. Procedures and variables

7.1 Schedule of procedures

7.1.1 Tabulated overview

Table 7–1 provides a tabulated overview of the study schedule of procedures.

Table 7–1: Schedule of Events

| Assessments | Eligibility & Screening (-30 days) | NovaSure EA Procedure (Day 0) | One-Week Post-EA Office Visit (± 2 days) | One-, Two-, and Three-Year Post-EA Phone Call (± 28 days) |
|--|---|--------------------------------------|---|--|
| Informed Consent Signature | X | | | |
| Inclusion / Exclusion Criteria | X | X ^a | | |
| Medical and Gynecologic History | X | | | |
| Essure Confirmation Test Results Confirmed | X | | | |
| Physical Exam and Vitals | X | | X | |
| Pelvic Exam | X | | | |
| Urine Pregnancy Test | | X ^a | | |
| NovaSure Procedure | | X | | |
| Pregnancy Status Inquiry | | | | X |
| Adverse Event Inquiry | | X ^b | X | X |
| Extirpative Surgery Inquiry | | | | X |
| Subject Interview | X | X ^b | X | X |
| Subject Contact Information Confirmed | X | X ^b | X | X |
| Study Completion / Early Termination Form | | | | X ^c |

Abbreviations: EA = endometrial ablation

a Assessment should be performed prior to NovaSure ablation

b Assessment should be performed following NovaSure ablation

c Complete the relevant form as necessary

7.1.2 Timing of assessments

7.1.2.1 Eligibility and Screening Visit (-30 days) - *amended*

As would normally occur, the subject will visit the physician seeking treatment for menorrhagia. After the subject decides to undergo the NovaSure procedure, the physician or designated site staff will:

- Inform the subject of the Essure-NovaSure PAS. Subject will not enroll in the study until she has a successful Essure confirmation test that documents bilateral satisfactory device location and fallopian tube occlusion noted on HSG OR optimal or satisfactory micro-insert location noted on TVU. If subject has had Essure placement but she does not have an Essure Confirmation Test that documents bilateral satisfactory device location and fallopian tube occlusion on HSG OR optimal or satisfactory micro-insert location on TVU, she may repeat the Essure Confirmation Test.²⁶
- If subject is eligible, the physician or designated site staff will administer the Informed Consent with the subject and answer any questions the subject has.
- If subject agrees to proceed with the study, subject and physician or designated site staff will each sign and date the informed consent, and, the subject will receive a signed copy.
- After having signed the Informed Consent (not before), subject will be asked all of the PAS Inclusion and Exclusion Criteria questions to verify that subject is eligible for the study. No study procedures (including asking questions) will be done without the subject having signed the Informed Consent.
- The subject will then be asked a number of demographic and medical history questions.
- Subject will then undergo a brief physical and pelvic exam.
- If subject continues to meet screening criteria, the subject should be scheduled for the NovaSure EA procedure.

In order to minimize PAS loss to follow-up, during the Site Initiation visits, the sponsor's staff, or designee(s), will instruct the PAS Investigators and their respective Study Staff to obtain the following subject information at Screening Visit: subject email addresses, both cell and home telephone numbers, and the same contact information of at least two close relatives (e.g., spouse, sister, etc) and two close acquaintances. They will also be instructed to confirm contact information at each visit/follow-up telephone call. Thus, although the actual contact will take place by telephone, each PAS site will have multiple methods of contacting the subjects to schedule a telephone contact.

7.1.2.2 NovaSure EA Procedure (Day 0)

The Investigator or designated study staff will confirm that the subject has not experienced an adverse event since the Eligibility and Screening Visit.

²⁶ TVU confirmation testing criteria added per Amendment 6

The NovaSure procedure will be performed in accordance with the NovaSure EA IFU and Controller Operator's Manual.

At the time of the procedure, subject's uterine cavity will be assessed to ensure that uterine cavity length is not less than 4 cm and uterine cavity width is not less than 2.5 cm (see Exclusion criteria 8; Section 5.1.2)²⁷; if they are, subject is ineligible to participate in the study.

7.1.2.3 One-Week Post-NovaSure EA Office Visit (\pm 2 days)

One week (plus or minus two days) from the date of NovaSure EA, the subject will return to the physician's office. At that time, designated study staff will conduct the following assessments:

- Physical Exam (Vitals)
- Inquire whether or not any adverse events occurred since the NovaSure procedure
- Conduct subject interview to obtain information on subject satisfaction and comfort with wearing the Essure micro-inserts post-NovaSure EA
- Confirm subject contact information
- Discuss any additional issues subject or the Investigator may have

7.1.2.4 One-, Two- and Three-Year Post-EA Phone Call (\pm 28 days) - *amended*

One, two-, and three- years (\pm 28 days) from the date of the NovaSure EA procedure, the subject will be contacted by the physician's office to have a telephone follow-up visit. During each of these visits, designated study staff will conduct subject interview to:

- Confirm subject is not currently pregnant or has not been pregnant in the previous year
- Inquire whether or not any adverse events occurred over the past year
- Conduct subject interview to obtain information on subject satisfaction and comfort with wearing the micro-inserts post-NovaSure EA procedure
- Discuss whether or not subject has had or will have any extirpative surgery
- Confirm subject contact information
- Discuss any additional issues subject or the Investigator may have

The 3-year phone call will be the final visit in the study. If the subject reports a serious adverse event or pregnancy during the 3-year follow-up phone call, the subject will be followed by the sponsor's pharmacovigilance department until event resolution or stabilization. If a pregnancy or serious adverse event was previously reported but the event is not resolved during the 3-year phone call, the event will be followed by the sponsor's

²⁷ Per Amendment 4

pharmacovigilance department until resolution. Information pertaining to these events will be collected and archived in the sponsor's pharmacovigilance database.²⁸

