The principal investigator of each center must sign the protocol signature sheet before subject recruitment may start at the respective center. Likewise, all protocol amendments/integrated protocols must be signed and dated by the principal investigator before coming into effect at the respective center.

A complete list of all participating centers and their investigators, as well as all required signature documents, will be maintained in the sponsor study file.

All other study personnel not included in this section are identified in a separate personnel list (not part of this clinical study protocol) as appropriate. This list will be updated as needed; an abbreviated version with personnel relevant for the centers will be available in each center’s investigator site file.

The global sponsor of this study is identified on the title page of this protocol. If required by local law, local co-sponsors will be nominated; they will be identified on the respective country-specific signature pages.

⁹ Per Amendment 4

¹⁰ Language regarding the Essure confirmation test was aligned with the IFU per Amendment 6.

¹¹ New section from sponsor template per Amendment 4

4. Study design

Design overview

This PAS is a prospective, multi-center, single-arm observational study to monitor and evaluate the effectiveness and safety of Essure when NovaSure is performed following a successful Essure Confirmation Test. The PAS will be conducted at up to 30 sites¹² in the United States. Each site may enroll a maximum of 35¹³ subjects. A minimum of 220 female subjects will be enrolled in the study. Subjects will be followed for a total of 3 years post-NovaSure EA with evaluations to occur at the 1 week, 12 month, 24 month and 36 month follow-up time points. PAS subjects who have been identified as candidates for NovaSure EA and have had a successful Essure Confirmation Test will be considered.

At least 50% of the subjects enrolled in the study must be 45 years of age or younger.

End of study

The primary outcome will be collected after last patient - last visit (LPLV). The end of the study as a whole will be the date when the clean data base is available.

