7.4.1.3 Assessments and documentation of adverse events³⁸ - amended

Investigators must collect all AEs for each subject from the time of signing of the informed consent through the end of subject study participation, whether or not deemed related to the investigational device or procedure. All AE data will be recorded on the CRFs as well as documented in the subject's medical record and study source documents.³⁹

All SAEs and SADEs will be followed until the event has subsided or, in case of permanent impairment, until the event stabilizes and the overall clinical outcome has been ascertained.

Investigator must determine whether adverse event meets the definition of a serious adverse event; if so, it must be reported as required by Section 7.4.1.1.

Any SAE or incident will be reviewed and processed by the sponsor according to all applicable regulations.

Investigators must document all device failures, malfunctions and use errors, including the assessment of whether the event is considered an incident (ADE) using the Device Malfunction and Failure CRF.

Because an approved device will be used for the placement procedure, any device malfunctions will be reported to the sponsor's Product Surveillance department. Device malfunctions will not be analyzed as part of this study as the placement procedure and devices are not being evaluated.

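### The annual calls ask about adverse events and pregnancy over a fixed past year, so a late or missed call leaves follow-up time that no scheduled question covers

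*Protocol*

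**What the plan says.** Protocol Section 7.1.2.4 schedules telephone calls at one, two and three years after NovaSure, each within 28 days either side. Two of the interview items carry a fixed look-back. For AEs, staff are to "Inquire whether or not any adverse events occurred over the past year". For pregnancy, they are to "Confirm subject is not currently pregnant or has not been pregnant in the previous year". The synopsis (Methodology) repeats both limits.

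Other items are anchored differently. At the one-week visit (Section 7.1.2.3) staff "Inquire whether or not any adverse events occurred since the NovaSure procedure", and on the day of ablation (Section 7.1.2.2) they check for events since screening. The surgery item in Section 7.1.2.4 has no time limit.

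Section 4 plans "evaluations to occur at the 1 week, 12 month, 24 month and 36 month follow-up time points", so nothing is scheduled between one week and one year. Table 7-1 places the AE inquiry on the procedure day, at one week and at the annual calls. It places the "Pregnancy Status Inquiry" at the annual calls only.

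Section 7.4.1.3 sets the general duty: "Investigators must collect all AEs for each subject from the time of signing of the informed consent through the end of subject study participation". Neither the Protocol nor the SAP defines the past year as the time since the last contact.

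**The concern.** The look-back has a fixed length, but the interval between contacts does not. Whenever a call comes more than 365 days after the previous contact, the difference lies outside the stated question. This can happen to a woman with every visit in window, and it happens on a larger scale when a call is missed. Section 5.2.1 keeps a woman who is lost and then re-contacted in the study, and Protocol Section 8.4.1 and SAP Section 6.2.1 count her whole participation as woman-months.

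AE incidence is the secondary endpoint and pregnancy the primary one. Events in an uncovered stretch reach the database only if the subject volunteers them or the site asks more widely than the text requires. Any resulting bias is towards fewer events.

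**Working it through.** The plan gives no figure of its own here, so the check is interval arithmetic on the visit windows.

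**Inputs**
- One-week visit: day 7 ± 2, so days 5-9 (Section 7.1.2.3).
- Annual calls: 365, 730 and 1,095 ± 28, so days 337-393, 702-758 and 1,067-1,123 (Section 7.1.2.4).
- Look-back: one year, read as 365 days (assumption).

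**Formula**

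Uncovered time = max(0, call day − 365 − day of previous contact). This is an interval length; the number of whole days strictly between the two points is one fewer.

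**First call, AEs**
- A call on day 393 looks back to day 393 − 365 = 28.
- Visit on day 5: 28 − 5 = 23 (days 6-27 unasked). Visit on day 7: 28 − 7 = 21 (days 8-27). Visit on day 9: 28 − 9 = 19 (days 10-27).
- The gap opens once the call is later than 365 + visit day, that is, day 370 to 374.

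**Between annual calls**
- Longest in-window interval: 758 − 337 = 421 days (also 1,123 − 702 = 421).
- Uncovered: 421 − 365 = 56 days.

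**Missed call**
- First call missed, second call made in window: from 702 − 365 − 9 = 328 to 758 − 365 − 5 = 388 days. On nominal dates, 730 − 365 − 7 = 358.
- Second call missed, third made in window: from 1,067 − 365 − 393 = 309 to 1,123 − 365 − 337 = 421 days. On nominal dates, 1,095 − 365 − 365 = 365.

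**How often, if visit and call days are independent and uniform within their windows (assumption)**
- The call window holds 57 days. For a visit on day v, 28 − v of them produce an early gap. Over v = 5 to 9 these counts are 23, 22, 21, 20 and 19, with mean 21. The probability is 21/57 = 0.37.
- Mean early gap when present: (276 + 253 + 231 + 210 + 190)/(23 + 22 + 21 + 20 + 19) = 1,160/105 = 11.0 as an interval, or about 10 whole days. Averaged over all women: 1,160/(5 × 57) = 4.1 days.
- For any given pair of consecutive annual calls: probability of a gap 28/57 = 0.49; mean when present (57 + 1)/3 = 19.3 days; mean over all women 0.49 × 19.3 = 9.5 days.
- Total over three years: 4.1 + 9.5 + 9.5 = about 23 days. A simulation of 400,000 schedules gave the same mean, with about 95% of women having at least one AE gap of some length.

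**Check on nominal dates**

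With contacts exactly on days 7, 365, 730 and 1,095, the uncovered AE time is zero.

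**The case against.** The strongest reply is that Section 7.1.2.4 lists interview topics and is not a script. The case report form is not attached (Section 14), so the wording put to the subject cannot be seen. The past year is natural shorthand for the time between nominally annual calls, and nominal dates leave no gap. Section 7.4.1.3 already requires all AEs, Table 7-1 lists the inquiry without a look-back, and each call ends with an open item for other issues. A woman phoned at 13 months is unlikely to cut her recall at day 28, and an AE still present when the look-back begins is captured. SAP Section 4.3 tells sites to pursue missed assessments. AE incidence carries no hypothesis (Section 8.4.2).

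On pregnancy the reply is stronger still. The call also asks about current pregnancy, and any pregnancy continuing into the look-back year is caught. A urine test precedes ablation (Table 7-1). Section 7.1.2.5 tells subjects to contact the investigator at once if they think they may be pregnant. Ectopic pregnancy and spontaneous abortion are always serious adverse events, reportable within 24 hours of the investigator's awareness (Sections 7.4.1.1.2 and 7.4.1.4).

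Most of this stands, and it limits the size of the point. The documents do not show that events in these stretches are never asked about, and no count of lost AEs can be derived. The reply does not remove the point, though. Section 7.4.1.3 states a duty but gives no look-back that would meet it, so wider questioning is left to each site. Section 7.1.2.5 gives no instruction to call about AEs in general. Pursuing missed visits does not change what the next completed call asks.

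**Conclusion.** The concern holds in a limited form. As written, the annual questions do not deliver the complete AE collection that Section 7.4.1.3 requires. For women with every contact in window, the uncovered time is at most about 23 days after the one-week visit and 56 days between consecutive annual calls. For a woman who misses a call and is later reached, it is about a year. The consequence is modest under-ascertainment of AEs. The day counts rest on reading a year as 365 days, and the frequencies on uniform call dates.

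Three stronger readings are tempting but not supported:
- **That the 421-day interval exposes weeks 2-4 after NovaSure.** It does not. That interval lies between two annual calls. The early gap comes from a late first call, 384-388 days after the one-week visit at most, and the full stretch to day 27 is uncovered only when that call falls on the last day of its window.
- **That the primary endpoint is materially biased.** Unasked calendar time does not measure missed pregnancies. Only a pregnancy that ends before the look-back starts and is not volunteered escapes. The plan's table for 200 women does show an upper limit of 0.012 with no failures and 0.023 with one, against a threshold of 0.021. One missed pregnancy could therefore matter under the SAP's 97.5% criterion, but nothing in the documents indicates that this wording would lose one.
- **That the early gap is the period of greatest complication risk.** Neither document gives a figure for when complications occur.

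**What to change.** In Section 7.1.2.4 and the synopsis, ask about AEs and pregnancy *since the last completed study contact*, with site staff reading that date to the subject. At the first completed annual call, ask about pregnancy *since the NovaSure procedure*, because the one-week visit has no pregnancy inquiry. Make the same change in the case report form or call script if it repeats the current wording.

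Every in-window gap then becomes zero, and a missed call is covered at the next completed one. The cost is a wording change and a slightly longer recall period for some women. No extra visit, call or subject is needed.
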